6.2 Rescue Medication

In order to treat BK viremia, prior to randomization, (ie, prior to screening, during the screening period and at the Baseline Visit), Investigators are permitted to decrease or alter immunosuppressive therapy per their discretion and/or per standard of care at their site. However, in the first 4 weeks after randomization, Investigators should refrain from additional changes in immunosuppressive regimen in response to BKV unless the viral load has increased by ≥ 1 log and the Investigator determines that a change is in the best interest of the patient.

Additional rescue medication including cidofovir, leflunomide and IVIG is strongly discouraged. However, if 4 weeks after randomization, the Investigator feels the subject is failing study drug and the subject is at significant risk of graft damage, and that additional medications are required for the subject's care, the Investigator may add additional therapies at their discretion.

Regardless of the use of rescue medication (changes in immunosuppressive regimen or addition of anti-viral medication), all subjects should complete study infusion(s) as long as they are tolerating the study drug.

6.3 Documentation of Prior and Concomitant Medication Use

The Investigator must instruct the subject to notify the study site about any new medications he/she takes after the subject was enrolled into the study.

All prescription medications; including over-the-counter drugs and significant non-drug therapies (including blood transfusions) received by the subject within 10 days prior to the initial dose of study drug administration and any concomitant medications used through the Follow-Up Visit will be recorded in the source documents and on the appropriate eCRF. In addition, all immunosuppressive therapy received since kidney transplantation (including the induction regimen) will be recorded.

6.4 Infusion Reactions

Although not previously reported following administration of MAU868, infusion reactions and infusion associated symptoms may occur following infusion of a monoclonal antibody due to sensitization due to the antibody or to the excipients in the infusion materials.

Symptoms indicative of anaphylaxis, or (based on CTCAE version 5 classification) Grade 3 or higher infusion reaction, Grade 2 or higher cytokine release syndrome, or Grade 2 or higher serum sickness should result in immediate halting of the infusion and prompt initiation of appropriate therapy. Subjects should not be re-challenged with study drug. Study drug should be permanently discontinued, but the patient should remain in the study for continued follow-up. Milder symptoms that do not meet criteria for immediate discontinuation from study drug may be managed by drug interruption and symptom management. The infusion should be temporarily stopped and the subject assessed. Diphenhydramine 50 mg and acetaminophen 650 mg should be administered. If symptoms improve after 30-60 minutes, the subject may be re-challenged with a reduced infusion rate of approximately 50% the initial rate. Medication(s) to treat gastrointestinal symptoms may also be given if needed. If the subject tolerates a re-challenge, they should receive pre-medication

with diphenhydramine 50 mg and acetaminophen 650 mg administered approximately 30-60 minutes prior to start of the next scheduled infusion. Subsequent infusions should be administered at a slower rate. For subsequent infusions of 1350 mg, study drug should be administered over approximately 120 minutes (2 hours). For subsequent infusions of 6750 mg, study drug should be administered over approximately 240 minutes (4 hours).

It is expected that the clinical site will have adequate facilities at the location of the study drug infusions to effectively manage and treat infusion reactions promptly.

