4.1 Treatment Groups

Subjects entering Cohort 1 will be randomized to 1 of 2 treatment arms in a ratio of 2:1 (MAU868:placebo):

- MAU868 1350 mg every 28 days for a total of 4 doses
- Placebo every 28 days for a total of 4 doses.

Subjects entering Cohort 2 will be randomized to 1 of 2 treatment arms in a ratio of 2:1 (MAU868:placebo):

- MAU868 6750 once and 1350 mg every 28 days for a total of 4 doses
- Placebo every 28 days for a total of 4 doses.

Subjects entering Cohort 3 will be randomized to 1 of 2 treatment arms in a ratio of 2:1 (MAU868:placebo):

- MAU868 6750 mg every 28 days for a total of 4 doses
- Placebo every 28 days for a total of 4 doses.

Minimum duration of the infusion for 6750 mg is at least 180 minutes and for 1350 mg is at least 60 minutes. All infusions will be followed by at least a 25 mL D5W flush to run at the same infusion rate as the dose of study drug.

A Pharmacy Manual will provide instructions for preparation of the infusion. The study drug is prepared as a dilution of the 450 mg/3mL stock solution in a total volume of 250 mL D5W. The investigational product is to be stored at 2° to 8° Celsius, protected from light and not shaken.

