5.3 Study Drug Administration

Study drug should be administered only at clinical sites. All clinical sites must have the appropriate equipment and trained personnel needed to effectively manage hypersensitivity reactions including anaphylaxis and infusion reactions.

Cohort 1 MAU868 Arm:

- MAU868 1350 mg IV over at least 60 minutes approximately every 28 days for a total of 4 doses.

Cohort 2 MAU868 Arm:

- MAU868 6750 mg IV over at least 180 minutes on Study Day 1, then 1350 mg IV over at least 60 minutes for subsequent doses approximately every 28 days for a total of 4 doses.

Cohort 3 MAU868 Arm:

- MAU868 6750 mg IV over at least 180 minutes approximately every 28 days for a total of 4 doses.

Placebo

- Cohort 1: Placebo (D5W) will be administered as an IV infusion over at least 60 minutes approximately every 28 days for a total of 4 doses.
- Cohort 2: Placebo (D5W) will be administered as an IV infusion over at least 180 minutes on Day 1 and then over 60 minutes approximately every 28 days for a total of 4 infusions.
- Cohort 3: Placebo (D5W) will be administered as an IV infusion over at least 180 minutes approximately every 28 days for a total of 4 infusions.
- Placebo is prepared as a standard 250 mL volume of intravenous fluid.

All infusions will be followed by at least a 25 mL D5W flush to run at the same infusion rate as the dose of study drug.

Refer to the Pharmacy Manual for additional dose preparation and administration instructions.

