5.3.1 Dose Adjustments and Interruption of Study Drug

Dose adjustments and interruptions of study drug are not permitted. Interruptions of individual infusions, however, are permitted in the event venous access becomes compromised or a subject is not tolerating the infusion ([Section 7.3.1](#)). The details of any interruption of an infusion, including the reason(s), the timing, and the resumption and completion of the infusion if applicable, must be recorded in the source documents and the eCRF.

For subjects who may require a hemodialysis, plasmapheresis, or immunoabsorption treatment, it shall be assumed that the study drug has been removed. A blood sample for PK analysis should be collected prior to and following these treatments. In the event that a subject requires hemodialysis, plasmapheresis, or immunoabsorption treatments; if <15 days since last MAU868/placebo treatment another dose will be given as soon as possible, and the next scheduled monthly dose skipped. Regular dosing will occur the following month. If the last dose was 15 days or greater no interim dose will be administered, and the regular monthly schedule will be followed. No subject will receive more than 4 doses. Subjects anticipated to require hemodialysis, plasmapheresis or immunoabsorption treatment at the time of randomization should not be randomized ([Exclusion Criterion 5](#)).

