7.3.1 Day 1 (Baseline; Study Drug Infusion 1)

The day on which the subject receives their first study drug infusion will be designated Day 1 (Baseline).

The following procedures will be performed **prior to initiation of the study drug infusion**; see Schedule of Events ([Appendix A](#)):

- Review and record medical conditions.
- Review and record concomitant medications.
- Obtain subject weight
- Collect blood (serum and plasma) and urine samples for BKV testing, pharmacokinetics, immunogenicity, hematology, clinical chemistry, and urinalysis for analysis at central laboratories.
- Females of childbearing potential must have a negative urine or serum pregnancy test result within 96 hours prior to Baseline. If applicable, perform urine or serum pregnancy test.
- Record vital signs, including temperature, blood pressure, heart rate, respiratory rate, and oxygen saturation within 30 minutes prior to the initiation of the infusion.
- Perform electrocardiogram (12-lead).

The following procedures will be performed **after the initiation of the study drug infusion**; see Schedule of Events ([Appendix A](#)):

- Record vital signs, including temperature, blood pressure, heart rate, respiratory rate, and oxygen saturation approximately every 30 minutes (+/- 10 minutes) after the start of the infusion until at least 2 hours after completing the infusion. Vital signs may also be collected at any time during or after the infusion at the Investigator's discretion.
- Collect blood (serum) for pharmacokinetics within 30 minutes following the completion of the infusion and again within 3 to 6 hours after the end of the infusion.
- Review and record adverse events.
- Review and record any new concomitant medications.

It is expected that the clinical site will have adequate facilities at the location of the study drug infusions to effectively manage and treat infusion reactions.

If a subject has experienced an infusion reaction following an infusion of study drug, the Investigator should discontinue the infusion. If symptoms resolve promptly the infusion may be resumed at a slower rate. In this case, the Investigator is encouraged to continue the subject's participation in the study. If the subject continues in the study, future infusions should be administered at a slower rate and preceded by use of premedication.

Cohort 1: Study Drug Administration Day 1

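### Protocol 7.3.1 lets an infusion resume after some reactions for which 6.4, 3.3.2 and Appendix D require a permanent stop, and the fixed later durations in 6.4 are not always slower

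*Protocol*

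**What the plan says.** **Stopping.** Protocol 6.4 names four triggers: anaphylaxis, infusion reaction of Grade 3 or higher, cytokine release syndrome of Grade 2 or higher, and serum sickness of Grade 2 or higher. After these the infusion is halted and the drug permanently withdrawn: "Subjects should not be re-challenged with study drug". Section 3.3.2 makes discontinuation mandatory for the same list. Appendix D repeats the grade thresholds and also rules out re-challenge.

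**Resuming.** For milder symptoms, 6.4 calls for a pause and named medication. If there is improvement after 30 to 60 minutes, "the subject may be re-challenged with a reduced infusion rate of approximately 50% the initial rate". Section 7.3.1 (Day 1) deals with an infusion reaction of unspecified grade: "If symptoms resolve promptly the infusion may be resumed at a slower rate". It then encourages the investigator to keep the subject in the study.

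**Cross-references.** Section 5.3.1 says: "Interruptions of individual infusions, however, are permitted in the event venous access becomes compromised or a subject is not tolerating the infusion", and cites 7.3.1 there. The Day 28 and Day 56 sections (7.3.5, 7.3.8) refer to 6.4. The Day 1 and Day 84 sections (7.3.1, 7.3.10) do not.

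**Durations.** Section 4.1: "Minimum duration of the infusion for 6750 mg is at least 180 minutes and for 1350 mg is at least 60 minutes". No maximum is given. After a tolerated re-challenge, 6.4 asks for later infusions at a slower rate and then gives fixed times: about 120 minutes for 1350 mg, and "For subsequent infusions of 6750 mg, study drug should be administered over approximately 240 minutes (4 hours".

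**The concern.** Safety and tolerability is the primary objective, and 1.8 puts infusion-related reactions first among the potential risks. If two sections give different answers to whether a stopped infusion may be restarted, two sites can handle the same event in different ways and each can cite the protocol. The subject's safety is at stake first.

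The data are affected as well. SAP 7.4.1 tabulates infusion reactions and treatment-emergent events leading to discontinuation of study drug. In arms of 8, those counts would partly reflect which section a site had read.

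The fixed durations raise a lesser question: whether an instruction meant to slow the next infusion always does so.

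**Working it through.** **1. Stop or resume.** The sections side by side:

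| | 6.4, 3.3.2, Appendix D | 7.3.1 |
|---|---|---|
| Trigger | Events defined by type and CTCAE grade | Any infusion reaction, no grade |
| Above threshold | Permanent stop, no re-challenge | Not distinguished |
| Test for restarting | Milder symptoms only, improved after 30 to 60 minutes (6.4) | Symptoms resolve promptly |
| Restart rate | About 50% of initial (6.4) | Slower, no figure |
| Cited by 5.3.1 | No | Yes |

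The conflict needs an event that is above threshold, counts as an infusion reaction, and resolves promptly.

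- *Cytokine release syndrome, Grade 2.* Appendix D defines this by hypotension that fluids correct, or hypoxia that needs less than 40% oxygen. Either may clear quickly. Section 1.8 places the syndrome among infusion-related reactions.
- *Anaphylaxis.* Also placed there by 1.8, and a stop criterion in 6.4 and 3.3.2 whatever the speed of recovery.
- *Infusion reaction, Grade 3.* Appendix D gives three routes: prolonged, recurring after improvement, or hospitalization indicated. Prompt resolution excludes the first but not necessarily the other two.
- *Serum sickness.* Appendix D puts its onset at about 6 to 21 days, so it hardly bears on restarting the same infusion.

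The overlap is therefore not empty.

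**2. Weight in the tables.** Planned active subjects per cohort: 8. One subject managed under the other section changes that arm's discontinuation rate by 1/8 = 12.5 percentage points. The documents give no expected reaction rate, so the number of such subjects cannot be estimated.

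**3. Later durations.** Let D be the dose, T the first infusion's duration and t the fixed later duration. The initial rate is D/T, the same-day re-challenge rate is 0.5 × D/T and the later rate is D/t. Hence later/initial = T/t.

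At the minimum T:

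- 1350 mg: 1350/60 = 22.5 mg/min; half is 11.25; later 1350/120 = 11.25. Later/initial = 0.50.
- 6750 mg: 6750/180 = 37.5 mg/min; half is 18.75; later 6750/240 = 28.125. Later/initial = 0.75.

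For longer first infusions, which the stated minimums allow:

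| Dose | T (min) | t (min) | Later/initial |
|---|---|---|---|
| 6750 mg | 240 | 240 | 1.00 |
| 6750 mg | 300 | 240 | 1.25 |
| 1350 mg | 120 | 120 | 1.00 |
| 1350 mg | 150 | 120 | 1.25 |

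The fixed figure gives no slowing once T reaches t. Within a dose these ratios are the same in mL/min, because the volume is always 250 mL (4.1). Repeat 6750 mg infusions occur only in Cohort 3: "MAU868 6750 mg IV over at least 180 minutes approximately every 28 days for a total of 4 doses".

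**The case against.** The best defence is that 7.3.1 lacks a cross-reference and does not state an opposite rule. The stop criteria appear in the Synopsis, 3.3.2, 6.4, 9.1.4 and Appendix D, mostly as duties, whereas 7.3.1 only permits. A site that follows the whole protocol would stop. The prompt-resolution test also resembles Appendix D's Grade 2 infusion reaction, and the stop lists name cytokine release syndrome separately from infusion reaction. This has force and limits how often the conflict should arise. It does not remove it: 1.8 uses the broader meaning, and 5.3.1 directs the site to 7.3.1.

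On durations, 6.4 still says that later infusions should be slower and gives only approximate times, so running faster after a 300-minute start would breach its own sentence. The pharmacy manual, which is not among these documents, may also set the initial rates.

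Three stronger readings are tempting and are not supported:

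- *That the 240-minute figure contradicts the 50% re-challenge rate.* At a 180-minute start it is 28.125/18.75 = 1.5 times that rate. But the 50% applies to same-day re-challenge, and the 240 minutes to the next scheduled infusion after premedication. Section 6.4 nowhere requires the two to match.
- *That a slowed Cohort 3 infusion is still faster than an unslowed Cohort 1 infusion.* In mg/min it is (28.125 against 22.5). In mL/min the order reverses: 250/240 = 1.04 against 250/60 = 4.17.
- *That all 36 subjects are affected.* Only a subject with an above-threshold reaction that resolves promptly is. Section 6.4 notes that infusion reactions had not been reported before with MAU868, and 12 of the 36 are planned for placebo.

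**Conclusion.** The main point stands. As written, 7.3.1 permits resumption in cases where 6.4, 3.3.2 and Appendix D require a permanent stop, and 5.3.1 points to 7.3.1. The tests for restarting a milder reaction also differ. This rests on reading infusion reaction in the sense of 1.8; under a narrower reading the overlap shrinks to Grade 3 infusion reactions that qualify by recurrence or hospitalization. Few subjects are likely to be affected, but each carries 12.5 points of an arm's discontinuation rate in a trial whose primary objective is safety.

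The secondary point is smaller. The fixed later durations fail to slow the infusion only if the first one already took at least 240 minutes (6750 mg) or 120 minutes (1350 mg). The protocol allows this, but the documents do not show that it happens. At the 180-minute minimum the later 6750 mg infusion is slower, at 75% of the initial rate. The difference from 50% is a figure for the sponsor to confirm and not an error.

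**What to change.** The sponsor should reconcile Protocol 3.3.2, 5.3.1, 6.4, 7.3.1, 7.3.5, 7.3.8, 7.3.10 and Appendix D into one infusion-reaction rule. The same trigger events, the same test for restarting and matching cross-references should appear wherever the rule is used.

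It should separately reconcile the fixed later durations in 6.4 with the requirement for a slower rate and with first-infusion durations that have no upper limit, and confirm that the 75% and 50% figures for 6750 mg are both intended.

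Which stopping rule, rate or duration applies is for the sponsor to decide.

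The cost is wording in the protocol and the pharmacy manual. No new data are needed: infusion start and stop times, interruptions and rate changes are already recorded on the eCRF.

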7 STUDY PROCEDURES

7.1 Informed Consent

Eligible subjects may only be included in the study after providing written (witnessed, where required by law or regulation), IRB/IEC-approved informed consent.

Informed consent must be obtained before conducting any study-specific procedures (i.e., all of the procedures described in the protocol). However, assessments or procedures performed as standard of care may be used for the purposes of screening. The process of obtaining informed consent must be documented in the subject source documents.

Information about common side effects already known about the investigational drug can be found in the Investigator's Brochure (IB). This information will be included in the subject informed consent and should be discussed with the subject during the study as needed. Any new information regarding the safety profile of the investigational drug that is identified between IB updates will be communicated as appropriate. New information might require an update to the informed consent and then must be discussed with the subject.

Once the subject has signed the informed consent, the subject may enter the Screening Period of the study.

7.2 Screening Period

Subjects who have had their renal transplant within the previous year may be considered for participation and entrance into the Screening Period following signing of the consent. Subjects may, enter the Screening Period (pre-treatment period) of up to 10 days following signing of the consent. If a subject does not meet all criteria within the 10-day window they will be considered a screen failure.

No study-specific procedures or activities may be performed until the informed consent process has been completed and the subject has signed the Informed Consent Form. However, assessments or procedures performed as standard of care may be used for the purposes of screening. Once a subject has signed the Informed Consent Form for study participation, the subject enters the Screening Period.

See [Section 8](#), Study Procedures and Assessments.

During the Screening Period, the following activities will be performed:

- Review of Inclusion Criteria ([Section 3.2.1](#)) and Exclusion Criteria ([Section 3.2.2](#)).
- Review and record medical and surgical history and current medical conditions.
- Review and record concomitant medications (see [Section 6.1](#) Excluded Medications and/or Procedures, for a list of prohibited medications).
- Review and record subject demography.
- Review and record Kidney Donor Profile Index (KDPI).
- Perform urine or serum pregnancy test on women of childbearing potential only. Note: either serum or urine must be documented as negative within 96 hours prior to Baseline.
- Record vital signs, including temperature, blood pressure, heart rate, respiratory rate, oxygen saturation and height and weight.
- Perform physical examination.
- Review of local and/or central plasma BKV PCR results
- Review of Adverse Events after informed consent is signed.

If the subject meets all inclusion and has no exclusion criteria during the Screening Period, the subject may enter the randomization portion of the study.

7.3 Treatment Period (Day 1 to Day 84)

If the subject meets all inclusion and exclusion criteria, the subject may then be randomized to receive either MAU868 or placebo. Randomization should occur as soon as possible, but not longer than 10 calendar days, after the local qualifying sample was collected.

Subjects will be randomized to study drug in the ratio of 2:1 (MAU868: placebo).

During the treatment period, subjects will receive MAU868 or placebo approximately every 28 days (every 4 weeks) for 12 weeks (4 doses total). Urine and blood will be monitored for BKV DNA weekly by PCR for the first 6 weeks of treatment and then every other week until completion of treatment and at each follow up visit. During this time, BKV DNA by PCR will be tested at the central laboratory.

During the treatment period, subjects should be seen approximately every 7 days (+/- 3 days) during the first 6 weeks and approximately every 14 days (+/-5 days) for the duration of treatment. Subjects may be seen more often at the Investigator's discretion. Visit dates are determined from the Baseline Visit.

NOTE:

- After the first 4 weeks of treatment, the Investigator may request BK viral load (urine and blood) testing more frequently (e.g., weekly) than mandated by the protocol, if clinically indicated.

- Subjects should continue with the study drug (i.e., MAU868 or placebo) until the last scheduled dose, regardless of documented viremia, need for rescue therapy and/or changes in the subject's immunosuppressive regimen.

7.3.1 Day 1 (Baseline; Study Drug Infusion 1)

The day on which the subject receives their first study drug infusion will be designated Day 1 (Baseline).

The following procedures will be performed **prior to initiation of the study drug infusion**; see Schedule of Events ([Appendix A](#)):

- Review and record medical conditions.
- Review and record concomitant medications.
- Obtain subject weight
- Collect blood (serum and plasma) and urine samples for BKV testing, pharmacokinetics, immunogenicity, hematology, clinical chemistry, and urinalysis for analysis at central laboratories.
- Females of childbearing potential must have a negative urine or serum pregnancy test result within 96 hours prior to Baseline. If applicable, perform urine or serum pregnancy test.
- Record vital signs, including temperature, blood pressure, heart rate, respiratory rate, and oxygen saturation within 30 minutes prior to the initiation of the infusion.
- Perform electrocardiogram (12-lead).

The following procedures will be performed **after the initiation of the study drug infusion**; see Schedule of Events ([Appendix A](#)):

- Record vital signs, including temperature, blood pressure, heart rate, respiratory rate, and oxygen saturation approximately every 30 minutes (+/- 10 minutes) after the start of the infusion until at least 2 hours after completing the infusion. Vital signs may also be collected at any time during or after the infusion at the Investigator's discretion.
- Collect blood (serum) for pharmacokinetics within 30 minutes following the completion of the infusion and again within 3 to 6 hours after the end of the infusion.
- Review and record adverse events.
- Review and record any new concomitant medications.

It is expected that the clinical site will have adequate facilities at the location of the study drug infusions to effectively manage and treat infusion reactions.

If a subject has experienced an infusion reaction following an infusion of study drug, the Investigator should discontinue the infusion. If symptoms resolve promptly the infusion may be resumed at a slower rate. In this case, the Investigator is encouraged to continue the subject's participation in the study. If the subject continues in the study, future infusions should be administered at a slower rate and preceded by use of premedication.

Cohort 1: Study Drug Administration Day 1

The subject will receive their study drug infusion (MAU868 1350 mg or Placebo). The respective infusions will be delivered over at least 60 minutes. Following completion of the infusion (infusion bag completely emptied into the drip chamber) a 25 mL D5W flush is to infuse at the same infusion rate as the dose of IP. Start and stop times will be recorded on the eCRF.

Cohort 2: Study Drug Administration Day 1

The subject will receive their study drug infusion (MAU868 6750 mg or Placebo). The respective infusions will be delivered over at least 180 minutes. Start and stop times will be recorded on the eCRF. For subsequent doses the subject will receive their study drug infusion (MAU868 1350 mg or Placebo). The respective infusions will be delivered over at least 60 minutes. Following completion of the infusion (infusion bag completely emptied into the drip chamber) a 25 mL D5W flush is to infuse at the same infusion rate as the dose of IP. Start and stop times will be recorded on the eCRF.

Cohort 3: Study Drug Administration Day 1

The subject will receive their study drug infusion (MAU868 6750 mg or Placebo). The respective infusions will be delivered over at least 180 minutes. Following completion of the infusion (infusion bag completely emptied into the drip chamber) a 25 mL D5W flush is to infuse at the same infusion rate as the dose of IP. Start and stop times will be recorded on the eCRF.

7.3.2 Day 7

The following procedures will be performed at this visit; see Schedule of Events ([Appendix A](#)):

- Record vital signs (if visit performed in person), including temperature, blood pressure, heart rate, respiratory rate, and oxygen saturation.
- Review and record adverse events.
- Review and record concomitant medications.
- Collect blood (serum and plasma) and urine samples for BK viral load testing, viral resistance, and pharmacokinetics for analysis at central laboratories.

7.3.3 Day 14

The following procedures will be performed at this visit; see Schedule of Events ([Appendix A](#)):

- Record vital signs (if visit performed in person), including temperature, blood pressure, heart rate, respiratory rate, and oxygen saturation.
- Review and record adverse events.
- Review and record concomitant medications.
- Collect blood (serum and plasma) and urine samples for BK viral load testing, viral resistance, pharmacokinetics, hematology, clinical chemistry, and urinalysis for analysis at central laboratories

7.3.4 Day 21

The following procedures will be performed at this visit; see Schedule of Events ([Appendix A](#)):

- Record vital signs (if visit performed in person), including temperature, blood pressure, heart rate, respiratory rate, and oxygen saturation.
- Review and record adverse events.
- Review and record concomitant medications.
- Collect blood (serum and plasma) and urine samples for BKV testing, viral resistance, and pharmacokinetics for analysis at central laboratories.

